9.3.1 AE Follow up

All AEs occurring during the study are to be followed up in accordance with good medical practice until they are resolved, stabilized or judged no longer clinically significant or, if a chronic condition, until fully characterized. Any AEs that are considered drug-related (possibly related, definitely related) must be followed for 30 days, or to resolution, or until no improvement is expected, whichever occurs first.

9.3.2 Overdose

No information on treatment of overdose of Ampion™ is currently available. In the case of overdose the subject should be followed as for an AE and appropriate supportive medical treatment instigated.

9.4 SERIOUS ADVERSE EVENT REPORTING

9.4.1 Reporting Requirements

Unexpected serious suspected adverse reactions are subject to expedited reporting to FDA. ALL SAEs must be entered into the eCRF within 24 hours of first knowledge of the event by study personnel. It is important that the investigator provide his/her assessment of relationship to study drug at the time of the initial report. Entry of an SAE into the eCRF triggers an automatic alert to the CRO safety team. The following information must be reported:

- Protocol number
- Site and/or Investigator number
- Subject number
- Demographic data
- Brief description of the event
- Onset date and time
- Resolution date and time, if the event resolved
- Current status, if event not yet resolved
- Any concomitant treatment and medication
- Investigator's assessment of whether the SAE was related to Investigative product or not.

The CRO Safety Associate will contact the site for clarification of data entered onto the eCRF, or to obtain missing information. In the event of questions regarding SAE reporting, the site may contact the appropriate individual as in Section 9.4.2

9.4.2 SAE Contact Information

Ampio Pharmaceuticals Inc, or their designee CRO, is responsible for submitting reports of AEs associated with the use of the drug that are both serious and unexpected to FDA according to 21 CFR 312.32 and the final guidance (2012). All investigators participating in ongoing clinical studies with the study medication will receive copies of these reports for prompt submission to their Institutional Review Board (IRB) or Ethics committee (EC).

10 STATISTICAL METHODS

10.1 GENERAL CONSIDERATIONS

This section describes the rules and conventions to be used in the presentation and analysis of the data.

10.1.1 Statistical and Analytical Plan:

This is an open-label study to evaluate the safety of intra-articular Ampion™ every 12 weeks over a total course of 52 weeks (12 weeks in AP-003-C main study and an additional 40 weeks in AP-003-C-OLE study) in subjects with OA of the knee. Safety will be assessed by recording AEs at all visits, recording concomitant medications, physical exams, and vital signs at all in-clinic visits, and obtaining labs at the final study visit (Visit 17 or Early Termination Visit 18 only).

Efficacy of repeat injections will be analyzed as exploratory endpoints. Efficacy variables will be assessed at all in-clinic visits.

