| Objectives: The primary trial objective is to carry on from the AP-003-C main study (one injection) and evaluate the safety of a 4-mL intra-articular (IA) injection of Ampion™ with repeat dosing every 12 weeks for 52 weeks and/or with five total injections of Ampion™. The exploratory objectives are to analyze the efficacy of a 4-mL intra-articular (IA) injection of Ampion™ with repeat dosing every 12 weeks for 52 weeks and/or with five total injections of Ampion™. | | |

| Sponsor: Ampio Pharmaceuticals, Inc. | Investigational Product: Ampion™ | Developmental Phase: Phase 3 |
|--|--|--|
|--|--|--|

Methods:

Subjects who have completed the AP-003-C main study (n=161) will be offered the option to roll-over to the open label extension study (AP-003-C-OLE). At their final visit of the AP-003-C main study (Visit 7), subjects will be offered the option to participate in the AP-003-C-OLE study. Enrollment into the AP-003-C-OLE study (Visit 9) allows a 170-day screening window from the AP-003-C main study Visit 7.

AP-003-C-OLE study will include the following visits:

| | |
|----------|---|
| Visit 9 | Enrollment (Day 0 = Day 84 of AP-003-C main study \pm 170 days, but not to occur before completion of AP-003-C main study), in-office visit |
| Visit 10 | (24 hours after Visit 9), post injection follow-up telephone call |
| Visit 11 | Week 12 (Day 84 \pm 14 days), in-office visit |
| Visit 12 | (24 hours after Visit 11), post injection follow-up telephone call |
| Visit 13 | Week 24 (Day 168 \pm 14 days), in-office visit |
| Visit 14 | (24 hours after Visit 13), post injection follow-up telephone call |
| Visit 15 | Week 36 (Day 252 \pm 14 days), in-office visit |
| Visit 16 | (24 hours after Visit 15), post injection follow-up telephone call |
| Visit 17 | Week 40 (Day 280 \pm 14 days), in-office final visit |

The safety of repeat dosing will be evaluated at all visits; in-office visit safety assessments will include vital signs, physical exams, evaluation of AEs, and laboratory analysis (Visit 17, Week 40, visit only) and phone visits will evaluate for AEs.

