| 
replacement in the affected knee
 
7. Isolated patella femoral syndrome, also known as chondromalacia
 
8. Any other disease or condition interfering with the free use and evaluation of the index knee for the duration of the trial (e.g. cancer, congenital defects, spine osteoarthritis)
 
9. Major injury to the index knee within the last 12 months
 
10. Severe hip osteoarthritis ipsilateral to the index knee
 
11. Any pain that could interfere with the assessment of study knee pain (e.g. pain in any other part of the lower extremities, pain radiating to the knee)
 
12. Any pharmacological or non-pharmacological treatment targeting OA started or changed 4 weeks prior to entry into the AP-003-C-OLE study, or likely to be changed during the duration of the AP-003-C-OLE study
 
13. Pregnancy or planning to become pregnant during the study
 
14. Use of the following medications:
 
a. No IA injected pain medications in the study knee during the study. HA and steroid injections in the contralateral knee (non-study knee) are acceptable while on study except \pm 14 days of an Ampion injection in the study kneeb. No analgesics containing opioidsc. NSAIDs are not permitted \pm 72 hours before/after injections at in-office visits; acetaminophen is available as a rescue medication during the study from the provided supplyd. No topical treatment on the study knee during the studye. No significant anticoagulant therapy (e.g. Heparin or Lovenox) during the study (treatment such as Aspirin and Plavix are allowed)f. No systemic treatments that may interfere with safety or efficacy assessments during the studyg. No immunosuppressantsh. No use of corticosteroidsi. No human albumin treatment in the 3 months prior to the AP-003-C main study or interim period prior to enrollment into the AP-003-C-OLE study. No human albumin treatment throughout the duration of the AP-003-C-OLE study | | |
| 
Test Product, Dose and Mode of Administration:
 
Ampion™ 4-mL intra-articular injection in the knee
 | | |
| 
Reference Therapy, Dose and Mode of Administration:
 
Not applicable
 | | |
| 
Study Duration:
 
40 weeks
 | | |

| Sponsor: Ampio Pharmaceuticals, Inc. | Investigational Product: Ampion™ | Developmental Phase: Phase 3 |
|--|--|--|
| Main Study + Extension Study = 52 weeks | | |
| Criteria for Evaluation: | | |

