3 STUDY DESIGN

3.1 STUDY DESIGN OVERVIEW

Subjects who have completed the AP-003-C main study (n=161) will be offered the option to roll-over to the open label extension study (AP-003-C-OLE) at their final visit of the AP-003-C main study (Visit 7). Enrollment into the AP-003-C-OLE study (Visit 9) allows a 170-day screening window from the AP-003-C main study Visit 7. AP-003-C-OLE study will include the following visits:

Visit 9/Enrollment (Day-170 to Day 0, but not to occur before completion of AP-003-C main study) in-office visit, Visit 10 (24 hours after enrollment post injection follow-up telephone call), Visit 11 in-office visit (Day 84 ±14 days), Visit 12 (24 hours after Visit 11 post injection follow-up telephone call), Visit 13 in-office visit (Day 168 ± 14 days), Visit 14 (24 hours after Visit 13 post injection follow-up telephone call), Visit 15 in-office visit (Day 252 ± 14 days), Visit 16 (24 hours after visit 15 post injection follow-up telephone call), Visit 17 final in-office visit (Day 280 ± 14 days).

The safety of repeat dosing will be evaluated at all visits; in-office visit safety assessments will include vital signs, physical exams, evaluation of AEs, and laboratory analysis. Phone visits will evaluate for AEs.

The clinical effects of treatment on OA pain will be evaluated during all in-clinic visits using the Western Ontario and McMaster Universities Arthritis Index (WOMAC®) osteoarthritis Index 3.1 and the Patient's Global Assessment of disease severity (PGA). The WOMAC will also be utilized to assess the contralateral knee pain at Enrollment/Visit 9 and Visit 17 (or Early Termination Visit).

The WOMAC® is a validated pain scoring system and sets the standard for the subject response. In order not to bias the collection of data, only questions from the validated WOMAC pain scale will be asked of subjects.

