3.2 STUDY OBJECTIVES

3.2.1 Primary Objective

The primary trial objective is to carry on from the AP-003-C main study (one injection) and evaluate the safety of a 4-mL intra-articular (IA) injection of Ampion™ with repeat dosing every 12 weeks for 52 weeks and/or with five total injections of Ampion™.

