| Review Rescue medication ⁶ | X ⁶ | X | X | X | X | X | X | X | X | X |
| Adverse Events ⁷ | X | X | X | X | X | X | X | X | X | X |

1. Subjects have 170 days to roll over from the AP-003-C main study (Visit 7) to this AP-003-C-OLE study (Visit 9). The first injection of the AP-003-C-OLE study is considered "Day 0". Visit 8 is accounted for in the AP-003-C main study in the event of Early Termination.
2. WOMAC also assessed for contralateral knee at Visit 9 and Visit 17 (or Early Termination visit, if applicable).
3. X-ray as assessed during Screening of AP-003-C main study.

4. For women of child-bearing potential, a HCG urine analysis must be completed at Visit 9 prior to enrollment in AP-003-C-OLE study to verify subject is not pregnant.
5. Rescue medication provided at Visit 9 and then as needed throughout the study. Bottles must be collected prior to dispensing a new bottle and at termination of AP-003-C-OLE study.
6. Use of rescue medication should be reviewed during each visit.
7. AEs at Visit 9 should be evaluated for ongoing AEs from the AP-003-C main study (pre-injection) and AEs occurring after injection.
8. X-ray to be obtained at Visit 18 unless subject terminates in order to get TKR. X-ray is unnecessary in this case.

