- Change in contralateral knee pain (WOMAC A) between Visit 9 and Visit 17
- Change in contralateral knee stiffness (WOMAC B) between Visit 9 and Visit 17
- Change in contralateral knee function (WOMAC C) between Visit 9 and Visit 17
- Time to Total Knee Replacement (TKR)
- Use of rescue analgesia (amount of acetaminophen used)

Exploratory efficacy analyses include the mean change and percent change in WOMAC A, WOMAC B, WOMAC C, WOMAC A1-2, WOMAC A3-5, PGA and amount of acetaminophen used from Visit 1 to Visit 17 using an analysis of covariance model, adjusted for baseline value.

Percent responders using the OMERACT-OARSI responder criteria will be analyzed defined as the percent of subjects whom respond to treatment from Visit 1 to Visit 17. Interim visits will also be analyzed.

1. High improvement in pain or in function $\geq 50\%$ and absolute change in Likert pain scale of ≥ 1 OR
2. Improvement in at least two of the 3 following:
 - a. pain $\geq 20\%$ and absolute change in Likert score ≥ 0.5
 - b. function $\geq 20\%$ and absolute change in Likert score ≥ 0.5
 - c. subject's global assessment $\geq 20\%$ and absolute change in Likert score ≥ 0.5

All of the above endpoints will be evaluated via descriptive statistics and confidence intervals.

The WOMAC Pain Score, the WOMAC Function Score, then PGA score and the OMERACT-OARSI responder criteria, will be analyzed via a repeated measures analysis of variance to determine if there is a significant time effect for these endpoints. Also, to aid in the interpretation of these results, a stability analysis will be performed on these same endpoints. That is, mean pairwise differences between administration time points will be calculated along with their 95% confidence intervals. If stability is achieved at some time point, then the following mean differences should be not be different from zero, in that the confidence interval should include zero.

Adverse events will be tabulated for both number of subjects and number of events by subject and overall study population, summarized by any event, body system, and preferred term. Summaries by serious, severity, and relationship will also be done.

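### The 52-week, every-12-weeks description holds only with little or no roll-over gap, and no planned analysis separates subjects by gap, number of Ampion injections or exposure

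*Protocol*

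**What the plan says.** Protocol section 10.1.1 describes injections "every 12 weeks over a total course of 52 weeks (12 weeks in AP-003-C main study and an additional 40 weeks in AP-003-C-OLE study". The synopsis repeats the sum under Study Duration: "Main Study + Extension Study = 52 weeks". The primary objective (Protocol 3.2.1 and 10.2, SAP 2.1) is safety "with repeat dosing every 12 weeks for 52 weeks and/or with five total injections".

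Protocol 3.1 and SAP 2.3 allow a delay: "Enrollment into the AP-003-C-OLE study (Visit 9) allows a 170-day screening window from the AP-003-C main study Visit 7". Footnote 1 to Table 6.1 agrees: "Subjects have 170 days to roll over from the AP-003-C main study (Visit 7) to this AP-003-C-OLE study (Visit 9"). The same footnote makes the first extension injection Day 0, so all later visits move with the gap. The synopsis sets the nominal position as "Day 0 = Day 84 of AP-003-C main study" and attaches the 170-day allowance to it.

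The safety and ITT populations need one extension dose (Protocol 10.3.1, 10.3.2). No text makes a permitted gap a protocol violation, so the per-protocol set does not separate these subjects either. The table list in SAP section 7 has no table by gap, number of injections or exposure time. Time on study starts at the first main-study dose in Protocol 10.3.6, but at the first dose of this study in SAP 4.2.

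For efficacy, Protocol 10.4.2 plans a stability analysis in which "mean pairwise differences between administration time points will be calculated along with their 95% confidence intervals". SAP 4.1 plans differences in pain score between successive visits.

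**The concern.** The sum 12 + 40 = 52 has no term for the gap, yet the design permits one of up to 170 days. A subject who uses much of the window is not dosed every 12 weeks between injections 1 and 2, and has not completed the series at 52 weeks. That subject is pooled with subjects who rolled over at once. Subjects given saline in the main study are pooled with them too.

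The primary endpoint is the incidence and severity of TEAEs, and SAP 2.4 ties the anticipated number of subjects to guidance on long-term safety. The number who received the regimen named in the objective is therefore a central result, and nothing planned counts them.

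The stability analysis has a related weakness. Visit 9 supplies the score after injection 1, possibly 36 weeks after it. Visits 11, 13 and 15 are each scheduled 12 weeks after the preceding injection. The Visit 9 to Visit 11 difference can therefore mix re-treatment after a long break with stability under regular dosing.

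**Working it through.** **Inputs.** Main-study Visit 7 on Day 84 (nominal day from the synopsis; its own visit window is not in these documents). Gap *g* = 0 to 170 days (Protocol 3.1, Table 6.1). Extension injections on extension Days 0, 84, 168 and 252, and final visit on Day 280 (Protocol 5 and 5.1). Main-study allocation 6:1 (Protocol 1.2).

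**The plan's own figure.** At *g* = 0 the course is 84 + 280 = 364 days = 52.0 weeks, with 1 + 4 = 5 injections, all 84 days apart. The stated 52 weeks reproduces, but only with no gap.

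**With a gap.** On the main-study clock the injections fall on Days 0, 84+*g*, 168+*g*, 252+*g* and 336+*g*, and follow-up ends on Day 364+*g*.

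| *g* (days) | First interval (days) | Fifth injection | End of follow-up | Injections by Day 364 |
|---|---|---|---|---|
| 0 | 84 (12.0 wk) | Day 336 | Day 364 (52.0 wk) | 5 |
| 28 | 112 (16.0 wk) | Day 364 | Day 392 (56.0 wk) | 5 |
| 112 | 196 (28.0 wk) | Day 448 | Day 476 (68.0 wk) | 4 |
| 170 | 254 (36.3 wk) | Day 506 | Day 534 (76.3 wk) | 3 |

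**Cut-offs.** The fifth injection falls by Day 364 if 336 + *g* ≤ 364, so *g* ≤ 28. The fourth does if 252 + *g* ≤ 364, so *g* ≤ 112. The third always does, since 168 + 170 = 338. If Visits 13 and 15 take place 14 days early, the cut-offs become 42 and 126 days.

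**Share affected.** The documents do not give it, and it could be anywhere from 0% to 100%. Purely as an assumption, gaps spread evenly over 0-170 days would put (170 − 28)/170 = 84% above 28 days and (170 − 112)/170 = 34% above 112. Spread over 0-60 days, (60 − 28)/60 = 53% would exceed 28. Spread over 0-28 days, none would.

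**Saline first.** At 6:1, 161/7 = 23 of 161 subjects had saline in the main study. The arm sizes in SAP 2.4 (140 and 25) give a similar figure: 161 × 25/165 = 24.4. These subjects can receive at most four Ampion injections. Their nominal span from first Ampion dose to the final visit is 280/7 = 40 weeks, whatever the gap.

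**The case against.** The strongest reply is that the objective has two limbs joined by and/or. A subject given Ampion in the main study who rolls over late and completes the extension still receives five injections and meets the second limb. Duration is not lost either: nominally, completers from the main-study Ampion arm span at least 52 weeks from first dose. Injections 2 to 5 stay on a 12-week schedule, and Protocol section 5 describes the extension itself only as 12-weekly for 36 weeks. All of this stands. It does not rescue section 10.1.1 or the synopsis, which have no second limb, and no analysis reports either limb separately.

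A reader might infer that many subjects missed the named regimen, and that the study therefore cannot support its objective. The documents contain no gap data, so the first part is unproven. The second goes too far: subjects with little gap and main-study Ampion can support the full regimen if they are shown separately.

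A reader might also infer that pooling flatters tolerability. The direction is not determined. A gap lowers dose density, but Protocol 9.3 runs adverse event reporting from the first main-study injection to Visit 17, so a gap also adds time at risk. No visit is scheduled within the gap, so events in it may depend on recall at Visit 9.

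Two partial safeguards exist. SAP 4.1 also computes the efficacy statistics from the main-study baseline, and those changes do not depend on the Visit 9 score. The successive-visit differences still do. SAP section 7 says outputs are shown by treatment arm without defining the arm. If that means the main-study arm, it would separate saline-first subjects, but not subjects by gap.

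**Conclusion.** The point holds as a mismatch between a stated property of the regimen and what the schedule guarantees. On nominal days the permitted first interval is 84 to 254 days, up to 254/84 = 3.0 times the stated spacing. The course runs 52 to about 76 weeks, and the injections given in the first 52 weeks range from five down to three. About one in seven main-study subjects had saline first and cannot reach five Ampion injections at all. The pooled TEAE rate therefore cannot by itself be read as the rate under 12-weekly dosing for 52 weeks.

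This rests on Visit 7 falling on Day 84 and, for the saline share, on roll-over subjects mirroring the main-study allocation. The number of subjects affected and the direction of any bias in the safety result are unknown from the documents. The efficacy part concerns exploratory endpoints without formal hypothesis tests, and carries less weight.

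**What to change.** - **Reconcile the text.** The sponsor should reconcile the duration and regimen statements (synopsis, Protocol 10.1.1, objectives in both documents) with the 170-day window, and the two time origins (Protocol 10.3.6 and SAP 4.2). Which of them gives way is for the sponsor to settle.
- **Add exposure to the SAP.** Derive each subject's first interval, number of Ampion injections and weeks from first Ampion dose, and tabulate them.
- **Report TEAEs by limb, with rates per person-time.** Show (a) main-study Ampion subjects whose actual injection dates meet a pre-specified definition of 12-weekly dosing for 52 weeks; (b) subjects with five Ampion injections, whatever the duration; and (c) all others. Groups (a) and (b) can overlap, and the tables should say so.
- **Repair the stability analysis.** For main-study Ampion subjects only, use Visit 7 as the 12-week score after injection 1, assuming WOMAC and PGA were collected then. Otherwise show the Visit 9 to Visit 11 difference by gap length. For saline-first subjects the Visit 7 score follows saline and must not be used this way.

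The cost is SAP wording and a few tables. Extension injection dates are recorded under Protocol 8.1, and main-study dates should already exist. The downside is that any statement about the 52-week regimen will rest on fewer subjects, with a wider interval.

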10.2 STUDY OBJECTIVES

The primary trial objective is to carry on from the AP-003-C main study (one injection) and evaluate the safety of a 4-mL intra-articular (IA) injection of Ampion™ with repeat dosing every 12 weeks for 52 weeks and/or with five total injections of Ampion™.

The exploratory objectives are to analyze the efficacy of a 4-mL intra-articular (IA) injection of Ampion™ with repeat dosing every 12 weeks for 52 weeks and/or with five total injections of Ampion™. Exploratory efficacy will evaluate changes in pain, stiffness and function using the validated WOMAC 3.1 Index and PGA.

10.3 ANALYSIS POPULATIONS

10.3.1 Safety Analysis Population:

The safety analysis population is defined as all subjects who are enrolled in the AP-003-C-OLE study and receive at least one dose of study medication (Ampion™). Subjects will be analyzed as treated.

10.3.2 Intent-to-treat Population:

The intent-to-treat (ITT) analysis population is defined as all subjects who are enrolled and receive at least one dose of study medication (Ampion™). Subjects will be analyzed as treated.

10.3.3 Per Protocol Population:

The per protocol analysis population is defined as all subjects included in the ITT analysis who met all entry criteria and had no major protocol violations as determined by the sponsor prior to analysis. All efficacy analyses will be repeated in the per-protocol population. These analyses will be supportive of the ITT analysis. Subjects will be analyzed as treated.

10.3.4 Statistical Analysis of Exploratory Effectiveness Endpoint

Since there are multiple injections administered over time, the stability and/or improvement of WOMAC and PGA scores between successive administrations will be investigated.

10.3.5 Primary Hypotheses for Exploratory Endpoints

The evaluation of efficacy is an exploratory endpoint and as such no formal hypothesis testing will be performed against a threshold of success. However, since there are multiple injections administered over time, the stability of pain scores will be evaluated between successive administrations to determine if the difference is zero. This will be evaluated by utilizing two sided 95% confidence intervals.

